2.7 Future Directions

Neuroprotection is one if not the most important topic in stroke matters. In an acute ischemic event, damage can extend beyond to areas neighboring the hypoxic tissue leading to a more extensive injury; hypoxia and hypoperfusion generates a series of abnormal metabolic events at different points within the neuron. As a consequence, there is a massive liberation of free radicals that will not only add more damage to the cells and will create a vasoactive effect.

Preclinical studies in rats have shown neuroprotective properties of n-acetylcysteine (NAC) in ischemic models [37b]. NAC was previously shown to be protective in several animal models of reperfusion injury, even in cerebral ischemia. The exact mechanism of action of NAC mediated neuroprotection is unknown. NAC is reported to have an intrinsic scavenging effect through direct reaction with hydroxyl radicals. In addition, NAC was shown to inhibit nitric oxide (NO) formation, which is thought to be due to the inhibition on nitric oxide synthetase [80]. NO production indirectly correlates with ischemic brain injury, since NOS inhibitors and nNOS deficient mice are reported to exhibit diminished neuronal damage after experimental stroke. We intend to use ferumoxytol and gadolinium to assess CNS inflammation and ischemia, with the use of NAC and other thiols.

3 OBJECTIVES

3.1 Primary objectives

3.1.1 Group 1: To compare ferumoxytol MR with gadolinium “gold standard” enhanced MR in adults with dural, parenchymal based, demyelinating or vascular CNS disease. This will involve imaging of the brain or the spine. Optimum sequencing parameters of ferumoxytol MRI will be established.

3.1.2 Group 2: To compare ferumoxytol MR with gadolinium enhanced MR in adults with any of the following (alone or in combination): vasculopathy of carotids, aorta, arteries of the extremities; or thrombosis of intraabdominal, pelvic or extremity veins. This will include carotid and/or aortic and/or extremity MRA or MRV as well as high resolution carotid plaque and vessel wall imaging and analysis. Optimum sequencing parameters of ferumoxytol MRI will be established.

3.1.3 Group 3: To compare ferumoxytol MR with gadolinium enhanced MR in adults with cervical lymphadenopathy, to identify imaging characteristics of the various etiologies (e.g. reactive vs. metastatic lymph nodes). Optimum sequencing parameters of ferumoxytol MRI will be established.

3.1.4 To assess the utility of ferumoxytol in subjects with renal disease, or with an allergy to gadolinium, who should not receive gadolinium-based contrast agents: this includes those with a chronic GFR < 50 ml/min/1.73m², acute kidney injury, and prior renal or liver transplant.

3.2 Secondary Objectives

3.2.1. This study will also provide preliminary, descriptive data for the following secondary objective: To localize ferumoxytol particles with histology and electron microscopy in biopsy samples from a small subset of subjects in which biopsy is needed. Results will also be compared to a companion study of brain tumor imaging entitled “NCI-Sponsored multi-disciplinary study for MR imaging of intravenous superparamagnetic crystalline particle ferumoxytol in primary high-grade brain tumors and/or cerebral metastases

3.2.2. To assess side effects/safety of ferumoxytol when given during MRI.

3.2.3 To assess the time course of iron uptake and clearance (of the first ferumoxytol injection) in abdominal organs, such as the liver, spleen, pancreas and bone marrow by applying usual abdominal MR sequences at multiple time points (up to 6 months) after ferumoxytol injection in a subgroup of subjects. For this purpose a subgroup of 50 subjects will be recruited from primary groups 1, 2 and 3.

4 TRIAL DESIGN

4.1 Inclusion Criteria

4.1.1 Group specific inclusion criteria:

Group1: Subjects must have a radiological or histological diagnosis of dural or central nervous system (CNS) parenchymal based inflammatory, vascular or demyelinating lesions. This includes but is not limited to unknown lesions, meningioma, neuroma, stroke, multiple sclerosis (MS) or related diseases such as acute disseminated encephalomyelitis (ADEM). Subjects with a CNS inflammatory lesion that is suspicious for neoplasm or radiation induced inflammation (vasculitis) will also be included.

Group2: Subjects must have radiological suspected diagnosis of vascular CNS lesions such as ischemic stroke, TIA with suspected carotid embolic origin, or vasculopathy involving the carotids (including diagnosed carotid stenosis >50%), the aorta, the arteries of the extremities, or diagnosed thrombosis of the intraabdominal, pelvic or extremity veins.

Group3: subjects must have clinical or radiological diagnosis of enlarged cervical lymph nodes in which inflammatory processes (reactive lymph nodes) is part of the differentials.

Subgroup: any subject in a primary group who agrees to participate in the abdominal imaging portion of the study.

4.1.2 Subjects must be 18 years or older for inclusion in this study.

4.1.3 Subjects must have a Karnofsky of 30% or greater.

4.1.4 Subjects agree to follow up approximately 4-6 weeks after each infusion of ferumoxytol.

4.1.5 All subjects or their authorized representative must sign a written informed consent and give HIPAA authorization in accordance with institutional guidelines.

4.1.6 Sexually active women of child-bearing potential and men must agree to use adequate contraception (hormonal or barrier method of birth control; or abstinence) at the start of study treatment and for the duration of study treatment. Should a female become pregnant or suspect she is pregnant while participating in this study, she should inform her treating physician immediately.

4.2 Exclusion criteria

4.2.1 Subjects with clinically significant signs of uncal herniation, such as acute pupillary enlargement, rapidly developing motor changes (over hours), or rapidly decreasing level of consciousness.

4.2.2 Subjects who have a contraindication for MRI: metal in their bodies (a cardiac pacemaker or other incompatible device).

- 4.2.3 Subjects with known allergic or hypersensitivity reactions to parenteral iron, parenteral dextran, parenteral iron-dextran, or parenteral iron-polysaccharide preparations (Investigator's Drug Brochure, Combidex 2002; Advanced Magnetics Inc; Investigator's Drug Brochure, Code 7228; 2003 Advanced Magnetics Inc).
- 4.2.4 Subjects with known hepatic insufficiency or cirrhosis
- 4.2.5 Subjects with known or suspected iron overload (genetic hemochromatosis or history of multiple transfusions)
- 4.2.6 Subjects with symptoms or signs of hemodynamic instability.
- 4.2.7 HIV-positive patients on combination antiretroviral therapy are ineligible because of the potential for pharmacokinetic interactions with ferumoxytol.
- 4.2.8 Pregnant or lactating women are excluded from this study because of possible risk to the fetus or infant.
- 4.2.9 Subjects with three or more drug allergies from separate drug classes.
- 4.2.10 Subgroup only exclusion criteria: prior administration of ferumoxytol.

4.3 Pre-Screen

Subjects will be initially evaluated in a variety of OHSU clinics or the inpatient setting to determine their eligibility. Possible clinics include; neuro-oncology, stroke, multiple sclerosis, cardiology, cardiothoracic, vascular surgery, hematology clinics, or inpatient services to determine possible candidacy for the study by one or more of the clinical investigators. If study participation is appropriate and the subject fulfills the eligibility criteria, they will be invited to participate.

4.4 Subject Registration

Following appropriate pre-registration evaluation, a signed consent, HIPAA authorization, and completed eligibility checklist will be obtained. New subject registrations will be submitted to the study coordinator, who will record study data on all subjects entered into the study and complete subsequent forms.

4.5 Ferumoxytol Administration: Route and Dosing

Ferumoxytol will be injected intravenously in divided doses followed by a saline flush. The maximum total dose during the day 2 MRI will be 510mg Fe. Ferumoxytol will be diluted in normal saline (1:1 or 15mg/ml) to reduce T2* effects in the MR angiography. [126] The drug will be stored at room temperature (68-77° F) away from direct sunlight. The solution will be prepared and dispensed by the investigational drug pharmacist. It will be administered in an OHSU MR suite.

For acquisition of DSC-MRI data, ferumoxytol (5 ml=75 mg) will be injected at up to 3 ml/sec followed by a saline flush. This rate is required for adequate signal change during the dynamic imaging. When no DSC-MRI data is obtained (spine and Group 3, the rate of the first dose (5 ml=75mg) will be 1 ml/sec. The remainder of the dose will be given in a second (10 ml=150 mg) and third (19 ml=285 mg) injection at a lower flow rate, not faster than 1 ml/s. There will be a short break in time between the three injections to allow for assessment per sections 4.7.5 and 5.1. *The dilution and injection parameters of the ferumoxytol may be adjusted to obtain optimal signal changes on MRI/MRA and to decrease the possibility of an allergic reaction. Injection rate can be varied based on the participant's IV site, but the total dose will never exceed 510mg.*

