The potential use of ferumoxytol as an MRI contrast agent was evaluated in open-label feasibility studies, including one Phase I study (Protocol Number 7228-01) in healthy volunteers and two Phase II studies (Protocol Numbers 58,254-2 and 58,254-5) in subjects undergoing a diagnostic imaging procedure. In the combined studies, 70 imaging subjects were exposed to a single administration of ≤4 mg Fe/kg ferumoxytol. Results from these studies demonstrated that ferumoxytol was useful in visualizing the arterial circulation. Ferumoxytol has a long blood half-life, unlike the majority of other MRI contrast agents, enabling arterial and venous imaging for a period of several hours following injection.

March of 2015 FDA Black Box Warning: In March of 2015 the FDA placed a black box warning on ferumoxytol stating:

WARNING: RISK FOR SERIOUS HYPERSENSITIVITY/ANAPHYLAXIS REACTIONS

Fatal and serious hypersensitivity reactions including anaphylaxis have occurred in patients receiving Feraheme. Initial symptoms may include hypotension, syncope, unresponsiveness, cardiac/cardiorespiratory arrest.

- Only administer Feraheme when personnel and therapies are immediately available for the treatment of anaphylaxis and other hypersensitivity reactions.
- Observe for signs or symptoms of hypersensitivity reactions during and for at least 30 minutes following Feraheme infusion including monitoring of blood pressure and pulse during and after Feraheme administration.
- Hypersensitivity reactions have occurred in patients in whom a previous Feraheme dose was tolerated.

In the black box warning the FDA updated their recommendations of how ferumoxytol should be given. The option to give ferumoxytol (510mg) as a fast undiluted injection in approximately 1 minute has been removed. It was recommended that ferumoxytol (510mg) be given over at least 15 minutes. To accommodate for this, the dose of ferumoxytol will be given in three separate, fractionated doses. The rate of administration of the second and third doses will be slowed down to no faster than 1 mL/s.

Post-Marketing Safety

AMAG’s pharmacovigilance system proactively reviews spontaneous reports. Routine surveillance of events is performed daily and monthly signal detection and evaluation processes monitor and update the safety profile. To date the information received from the post-marketing setting is consistent with the known safety profile of ferumoxytol.

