Based on communication with AMAG Pharmaceuticals, manufacturer of ferumoxytol, all recommendations apply to iron replacement therapy where infusion rate and dilution do not impact efficacy. However, for an imaging indication certain infusion parameters are required to gain information, such as dynamic imaging. Increased infusion rate will only affect the first injection of 1 mg/kg, which is a small fraction of the full therapeutic dose, and therefore may minimally increase the risk of adverse reactions. The next two injections are given at a slower rate. The recommended 15 minutes has no scientific basis, it has been chosen arbitrarily. For MR imaging stopping the scanner for 15 minutes would be disadvantageous. Applying multiple injections, which is not the case with iron replacement therapy, may increase safety, compared to continuous injection. This may contribute to the fact that in our patient population only minor adverse reactions have been reported.

OHSU Toxicity Data

As of December 31st, 2015, a total of 671 infusions of ferumoxytol had been completed on 331 study subjects as part of OHSU's Blood Brain Barrier sponsored IRB approved protocols. The dose has ranged from 75 to 510 mg of ferumoxytol (0.5 to 11 mg/kg). In all these cases, ferumoxytol was given during MRI, using multiple IV bolus injections (1:1 diluted ferumoxytol, 3ml/s flow rate, with 20ml saline flush at the same flow rate.) In most studies the first 1mg/kg (or 75mg) was used for dynamic perfusion imaging; the remaining dose was injected in one or two subsequent bolus injections. The full 510mg was never given as a single injection. Within 42 days after ferumoxytol administration, there were 85 adverse events possibly, probably or definitely related to ferumoxytol. Among the 85 events, 43 patients had 1 event, 12 had 2 events, 3 had three events, one had 4 events and one had five events. 80% of the toxicity events occurred within 48 hours post ferumoxytol administration. There were no severe, grade 4 or 5 toxicities (CTCAE version 3 and 4) that were attributed to ferumoxytol. Table 2 shows the toxicities up to and beyond 48 hours. (Data has been published in AJNR in July of 2017).

Toxicity Category Attribute	Overall (<42 days)		Within 48 hours		>48 hours	
	# of events	Freq of events	# of events	Freq of events	# of events	Freq of events
Gastrointestinal	31	4.62%	23	3.43%	8	1.19%
Cardiac General	17	2.53%	17	2.53%	0	0.00%
Pain	17	2.53%	17	2.53%	0	0.00%

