5.1.6.4 Day 4 (1week post ferumoxytol injection) (at physician's discretion)

Scan type	Scan Time (min)
0. Setup/localizer/B0 shimming/B1 mapping	2
1. Axial T1-weighted (T1w) Spin Echo (SE)	4
2. Axial T2-weighted (T2w) Fast Spin Echo (FSE)	4
3. Axial T2*-weighted gradient-echo (GRE)	4

5.1.6.5 Subgroup - Abdominal Sequences: baseline, shortly after Fe, 24-28 hours after Fe, 1 week after Fe, 1, 2, 3 and 6 months after Fe

Additional abdominal sequences may be performed before and after ferumoxytol injection: single breath hold each.	
Setup/localizer/B0 shimming/B1 mapping abdomen	2
Axial T2-weighted single shot fast spin echo (SSFSE)	1
Axial T2-weighted fat saturated fast spin echo (BH FRFSE)	1
Axial diffusion weighted imaging (DWI) x 2. b value of 50 and 750	1
Axial T1-weighted spoiled gradient echo (in phase and out of phase)	1
Axial 3D T1 gradient echo for dynamic (LAVA) sequence	1
Coronal T2-weighted single shot fast spin echo (SSFSE)	1

The dose, dilution and injection parameters may be adjusted to obtain optimal signal changes, but will never exceed 510mg Fe.

The above detailed sequences are subject to change in order to acquire the best imaging results on the applied field strength.

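### The spine and Group 3 tables list the third ferumoxytol injection as 18 ml for 285 mg, but at the stated two-fold dilution 18 ml holds 270 mg and 19 ml is needed

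*Combined protocol and SAP*

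**What the plan says.** Section 4.5 sets the concentration: "Ferumoxytol will be diluted in normal saline (1:1 or 15mg/ml". It then gives three injections: 5 ml for 75 mg, 10 ml for 150 mg, and a "third (19 ml=285 mg) injection at a lower flow rate, not faster than 1 ml/s". The Day 2 total may not exceed 510 mg.

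The brain (5.1.1.2), carotid (5.1.3.2) and aortic (5.1.4.2) Day 2 tables repeat 19 ml for 285 mg. The lower-extremity tables (5.1.5) give no injection volumes.

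The spine (5.1.2.3) and cervical lymph node (5.1.6.2) Day 2 tables differ. Each specifies two-fold dilution and lists 5 ml (75 mg), 10 ml (150 mg) and then 18 ml, labelled 285 mg. The spine table gives a total of 510 mg. The lymph node table gives 510 mg as an upper limit.

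Two clauses allow adjustment. Section 4.5 says "The dilution and injection parameters of the ferumoxytol may be adjusted to obtain optimal signal changes on MRI/MRA"; lowering allergic risk is its second stated purpose. A note after the abdominal sequence table says "The dose, dilution and injection parameters may be adjusted to obtain optimal signal changes, but will never exceed 510mg Fe".

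**The concern.** In both tables the volume, the mass and the dilution of the third injection cannot all be right. If two of them are followed, the third is wrong. Someone working from the volume column gives less iron than the label says. Someone working from the mass has to change either the volume or the dilution.

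The practical stake is dose consistency. Spine and Group 3 subjects could receive a different dose from subjects whose tables list 19 ml. Brain and spine subjects both belong to Group 1, so the difference could arise within one study group.

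**Working it through.** **Inputs**
- Concentration: 15 mg Fe/ml after 1:1 dilution (section 4.5). This implies undiluted drug at 2 × 15 = 30 mg/ml.
- Volumes in section 4.5: 5, 10 and 19 ml. The brain, carotid and aortic tables agree.
- Volumes in the spine and lymph node tables: 5, 10 and 18 ml, with two-fold dilution.

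**Formula:** mass = volume × concentration.

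**Step 1. Reproduce section 4.5.**
- 5 × 15 = 75 mg
- 10 × 15 = 150 mg
- 19 × 15 = 285 mg
- Total: 34 ml × 15 = 510 mg

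All four figures reproduce exactly.

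**Step 2. Apply the same formula to the spine and lymph node tables.**
- Third injection: 18 × 15 = 270 mg, against a label of 285 mg
- Total: (5 + 10 + 18) = 33 ml × 15 = 495 mg

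**Step 3. Size of the shortfall.**
- 285 − 270 = 15 mg
- Share of the third injection: 15/285 = 5.3%
- Share of the total: 15/510 = 2.9%

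**Step 4. Could 18 ml be right at another concentration?**
- 285/18 = 15.83 mg/ml, which is not a two-fold dilution of 30 mg/ml.
- The first two injections in the same cells work out at 75/5 = 15 and 150/10 = 15 mg/ml, so the third would need a separate preparation. Neither table provides for one.

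**Step 5. What conflicts in each table.**
- Spine: 18 ml conflicts with both the 285 mg label and the 510 mg total.
- Lymph node: 18 ml conflicts with the 285 mg label only, since 495 mg is within an upper limit of 510 mg.

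**The case against.** The strongest reply is that this is a typing slip with no consequence. The same cells give the intended mass, section 4.5 and three other tables give 19 ml, and a careful reader can recover the right figure. If the volume is followed literally, the error is 15 mg on the low side, and 510 mg is a maximum. Section 6.1 plans mainly qualitative comparisons of ferumoxytol with gadolinium, stratified by pathology in Group 1. It plans no comparison of dose between imaging regions. All of this stands, and it is why the point is minor. It does not make the entry correct.

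A reader might draw a stronger inference from the adjustment clauses. The ceiling on the second and third injections is in ml/s, and no limit in mg Fe/s is stated. Less dilute drug could therefore meet the ceiling while delivering iron faster: 1 ml/s × 15 mg/ml = 15 mg Fe/s as planned, and 1 × 30 = 30 mg Fe/s if undiluted. Those two injections carry 150 + 285 = 435 mg, or 435/510 = 85.3% of the dose. Section 2.6.2 relies partly on slowing them: "The rate of administration of the second and third doses will be slowed down to no faster than 1 mL/s".

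The documents do not support treating this as a defect:
- Section 4.5 and the brain, spine and lymph node tables already pair two-fold dilution with a rate of at most 1 ml/s. Undiluted drug is proposed nowhere.
- The section 4.5 clause also names lowering allergic risk as a purpose, although the note after the abdominal table omits it.
- Section 2.6.2 reports 671 earlier site infusions given as multiple boluses of "1:1 diluted ferumoxytol, 3ml/s flow rate, with 20ml saline flush at the same flow rate". That is 3 × 15 = 45 mg Fe/s, above the hypothetical 30, and no severe, grade 4 or 5 toxicity was attributed to the drug.
- The investigational pharmacist prepares the solution, and section 8.3.1 requires an amendment for changes that affect subject safety.

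A cap of 15 mg Fe/s would turn the default into a limit. It would also restrict tuning in a study whose primary objectives include establishing optimum sequence parameters. That is a design trade-off.

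**Conclusion.** The 18 ml entry is wrong as written in the spine and Group 3 Day 2 tables. Followed by volume, it delivers 270 mg in place of 285 mg, and 495 mg in place of the 510 mg that the 19 ml schedule delivers. The shortfall is 15 mg: 5.3% of the third injection and 2.9% of the total. The calculation assumes the 15 mg/ml of section 4.5, which both tables restate as two-fold dilution.

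The point is minor. The cap is not breached, no safety harm follows and no planned analysis turns on the difference. The documents do not show which figure staff follow, so one cannot say that any subject received, or will receive, the lower dose. Nor do they support a finding that the freedom to adjust dilution makes the second and third injections unsafe.

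**What to change.** In sections 5.1.2.3 and 5.1.6.2, change the volume of the third injection from 18 ml to 19 ml. Both tables then agree with section 4.5: 5 + 10 + 19 = 34 ml, and 34 × 15 = 510 mg.

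The cost is one number in two tables. No procedure, sample size or analysis changes. No new limit on the adjustment clauses is proposed.

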4.6 Study Groups

1. Group1: (n=up to 260) subjects will include those with dural, central nervous system (CNS) parenchymal based inflammatory, vascular or demyelinating lesions. This includes but is not limited to unknown lesions, meningioma, neuroma, stroke, multiple sclerosis (MS) or related diseases such as acute disseminated encephalomyelitis (ADEM). In these subjects the brain or the spine will be imaged.
2. Group2: (n=up to 25) subjects will include those with vascular CNS lesions such as ischemic stroke, TIA with suspected carotid embolic origin, or vasculopathy involving the carotids, (including diagnosed carotid stenosis >50%) the aorta, or the arteries of the extremities, or diagnosed thrombosis of the intraabdominal, pelvic or extremity veins. Carotid and/or aortic and/or extremity MRI and MRA or MRV will be performed in these subjects.
3. Group3: (n= up to 10) will include subjects with enlarged cervical lymph nodes in which inflammatory processes (reactive lymph nodes) is part of the differentials.
4. Subgroup: (n=50) will be comprised of subjects from any of the primary groups who agree to participate in the abdominal imaging portion of the study.

4.7 Study Visits, Procedures and Schedule of Events

Subject's need for anti-anxiolytics for each MRI study visit will be evaluated and administered as needed. Common anti-anxiolytics include lorazepam and diazepam; diphenhydramine may also be used. The administration of a relaxing/anti-anxiolytic agent will be given at the treating physician or the PI's discretion and is considered routine prior to MRI and as such is not being evaluated on this study.

4.7.1 Study Visit 1

4.7.1.1 Day 1 (gadolinium MRI)

The subject will have an anatomical MRI (brain &/or spine [group1], carotids and/or aorta and/or other arteries or veins [group2] or cervical lymph nodes [group3]) with and without gadolinium, which may include DWI, MRA or perfusion study. This MRI will be done

within 7 days prior to the ferumoxytol infusion and may have been done off study as medically necessary; and may or may not be repeated at PI's discretion. Laboratory testing (creatinine/GFR) to check kidney function and a pregnancy test in women of child bearing potential will be done prior to GBCA administration done on study. Subjects with renal insufficiency (GFR <50ml/min/1.73m²) and/or contraindication to GBCA, will not undergo imaging with gadolinium, they will proceed to "Day 2". Short abdominal MR imaging as a baseline will be performed in the subgroup prior to any ferumoxytol administration and may be done either day 1, or on day 2 prior to ferumoxytol administration).

